4.1 Number of Patients

Approximately 150 patients (30 per group) will be enrolled at approximately 15 sites in the US. Approximately 26 patients per group are expected to complete the study based on an anticipated dropout rate of less than 12.5%. Approximately two-thirds of the enrolled patients will be \leq 50 years old.

4.2 Study Population Characteristics

The study population will consist of adult patients who have objective and subjective evidence of presbyopia.

4.3 Inclusion Criteria

The following will be requirements for entry into the study:

1. Male or female, between 40 and 55 years of age

[REDACTED]

3. Natural or corneal laser refractive surgery corrected [REDACTED] at distance with presbyopia in each eye and subjective complaints of poor near vision that impact activities of daily living, [REDACTED]

[REDACTED]

[REDACTED]

[REDACTED]

[REDACTED]

[REDACTED]

[REDACTED]

[REDACTED]

[REDACTED]

Approval Date: 18-Aug-2016

[Redacted text block]

4.4 Exclusion Criteria

The following will be criteria for exclusion from the study:

Ophthalmic:

1. Concurrent use of any topical ophthalmic medications, including artificial tears, other than the study medications, during the course of the study

[Redacted text block]

4. Corneal abnormalities (including keratoconus, corneal scar, Fuchs' endothelial dystrophy, guttata, or edema) in either eye that are likely to interfere with visual acuity

5. History of cataract surgery, phakic intraocular lens (PIOL surgery), corneal inlay surgery, [Redacted text]

[Redacted text block]

Approval Date: 18-Aug-2016

[Redacted]

[Redacted]

10. Diagnosis of any type of glaucoma or ocular hypertension

[Redacted]

[Redacted]

[Redacted]

[Redacted]

[Redacted]

[Redacted]

[Redacted]

[Redacted]

[Redacted]

[Redacted]

[Redacted]

[Redacted]

[Redacted]

[Redacted]

[Redacted]

Approval Date: 18-Aug-2016

4.5 Permissible and Prohibited Medications/Treatments

4.5.1 Permissible Medications/Treatments

The concurrent use of nonocular medications that do not have a substantial effect on the pupil, accommodative properties, or retinal function of the eye will be permitted during the study if a stable dosing regimen is established. The dosing regimen is not considered to be stable if a patient starts, stops, or changes the dose/drug during the study.

4.5.1.1 Definition of Females of (Non-)Childbearing Potential and/or Acceptable Contraceptive Methods

For purposes of this study, females will be considered of childbearing potential unless they are naturally postmenopausal (see definition below) or permanently sterilized (ie, hysterectomy).

Natural menopause is defined as the permanent cessation of menstrual periods, determined retrospectively after a woman has experienced 12 months of amenorrhea without any other obvious pathological or physiological cause. For women of childbearing potential who may participate in the study, the following methods of contraception, if properly used, are generally considered reliable: oral contraceptives, patch contraceptives, injection contraceptives, male condom with intravaginal spermicide, diaphragm or cervical cap with spermicide, vaginal contraceptive ring, intrauterine device, surgical sterilization (bilateral tubal ligation), vasectomized partner, or sexual abstinence.

The investigator and each patient will determine the appropriate method of contraception for the patient during their participation in the study.

4.6 Prohibited Medications/Treatments

Use of ocular medications other than study medication or medications administered to conduct study procedures (see Section 6.4) are prohibited from the screening visit until study exit.

Use of medications that may have a substantial effect on visual function or the optical properties of the eye is prohibited 2 weeks prior to the baseline visit and during the study:

- systemic medications with potential ocular side effects, including topiramate, hydroxychloroquine, ethambutol, phosphodiesterase 5 (PDE5) inhibitors (sildenafil, vardenafil, tadalafil), or tamoxifen
- ophthalmic, systemic, or intranasal anticholinergics and α -adrenergic receptor agonists with potential pupillary or accommodative effects, including oxymetazoline, pilocarpine, tetrahydrozoline, phenylephrine, naphazoline, cyclopentolate, atropine, beta-blockers, or antihistamines
- systemic maprotiline, tricyclic antidepressants, or monoamine oxidase inhibitors (MAOIs)

The decision to administer a prohibited medication/treatment will be made with the safety of the study participant as the primary consideration. When possible, Allergan should be notified before the prohibited medication/treatment is administered.

5. Study Treatments

5.1 Study Treatments and Formulations

Fixed combination AGN-199201 [redacted] weight/volume (w/v) and AGN-190584 [redacted]
[redacted]
[redacted]
[redacted]

Fixed combination AGN-199201 [redacted] w/v and AGN-190584 [redacted]
[redacted]
[redacted]
[redacted]

Fixed combination AGN-199201 [redacted] w/v and AGN-190584 [redacted]
[redacted]
[redacted]
[redacted]

5.2 Control Treatment

The vehicle of AGN-199201 and AGN-190584 [redacted]
[redacted]
[redacted]

Approval Date: 18-Aug-2016

5.3 Methods for Masking

Study medication will be administered to each randomized patient bilaterally by qualified site personnel during the study visits 1 to 5. The patient will be instructed to continue using the dispensed study medication on the assigned eyes between visits. The investigator, investigational staff, and patients will be fully masked to study drug and vehicle treatments. All study treatments will be provided in identical multidose bottles and cartons.

5.4 Treatment Allocation Ratio and Stratification

Patients will be randomized in a 1:1:1:1:1 ratio into 1 of 5 treatment groups:

- Group 1: Vehicle control, OU
- Group 2: Fixed combination AGN 199201 (██████████) and AGN 190584 (██████████), OU
- Group 3: Fixed combination AGN 199201 (██████████) and AGN 190584 (██████████), OU
- Group 4: Fixed combination AGN 199201 (██████████) and AGN 190584 (██████████), OU
- Group 5: Fixed combination AGN 199201 (██████████) and AGN 190584 (██████████),
monocular dosing to the nondominant eye and vehicle to the dominant eye

Randomization will be stratified by age (2 groups: ≤ 50 and > 50) and iris color (2 groups: brown and not brown) at the baseline visit. There will be a total of 4 strata; brown eyes and age ≤ 50 years, brown eyes and age > 50 years, not brown eyes and age ≤ 50 years, and not brown eyes and age > 50 years. For the determination of stratification group assignment for each patient, sites will be required to enter iris color (ie, brown, blue, green, gray, or hazel) and age into the Interactive Response System (IxRS), and the IxRS will assign the stratum.

5.5 Method for Assignment to Treatment Groups/Randomization

Prior to initiation of study treatment, each patient who provides informed consent will be assigned a patient number that will serve as the patient identification number on all study documents.

At the time of randomization on visit 1, eligible patients will be placed into 1 of 4 strata as described in Section 5.4, and they will be assigned to 1 of the 5 treatment groups based on the randomization scheme within the patient's stratum according to the order of enrollment. The IxRS will assign the next available randomization number for the appropriate stratum to the patient at the time the investigator requests randomization. The IxRS will report a

medication kit number to use for each patient corresponding to the randomization number. The randomization scheme will be prepared by Allergan Biostatistics.

Study medication will be labeled with the medication kit number, study number, and dominant or nondominant eye. Each medication kit (carton) will contain 2 multidose bottles of study treatment. The IxRS will provide the site with the specific medication kit number(s) for each randomized patient at the time of randomization. Sites will assign study medication kits according to the IxRS instructions. Sites will receive the IxRS confirmation notifications for each transaction. All notifications will be maintained with the study source documents.

5.6 Treatment Regimen and Dosing

Doses of study medication and/or vehicle will be instilled in the appropriate eyes by designated site personnel at hour 0 (8 AM \pm 1 hour) of visits 1, 2, 3, 4, and 5. In between office visits, patients will be instructed to continue using the dispensed study medication on the assigned eyes in the morning QD.

Patients receiving the fixed combination of AGN-199201 and AGN-190584 bilaterally will instill a single drop of the fixed combination drug into each eye. Patients receiving the fixed combination of AGN-199201 and AGN-190584 in the nondominant eye only will instill a single drop of the fixed combination drug into the nondominant eye and a single drop of the vehicle into the dominant eye. Patients receiving vehicle bilaterally will instill a single drop of the vehicle into each eye (see Table 1 and Figure 1).

5.7 Storage of Study Medications/Treatments

The study product must be stored in a secure area. Only assigned study personnel, authorized by the investigator, may have access to study product. Study product will be administered only to patients entered into the clinical study, at no cost to the patient, in accordance with the conditions specified in this protocol.

All study products must be stored upright, in a refrigerator and protected from freezing. All study products will be stored within the temperature storage range limits required to ensure study product stability during the study. Sites must report any temperature excursion to Allergan, and avoid administering the impacted study product, by isolating the product, until receiving further instructions from Allergan (see Study Procedure Manual for more information).

Patients will be instructed on the proper storage of study medication and to keep it out of the reach of children at all times.

5.8 Treatment Administration

Doses of study medication and/or vehicle will be instilled in the appropriate eyes by designated site personnel at hour 0 (8 AM ± 1 hour) of visits 1, 2, 3, 4, and 5. In between office visits, patients will be instructed to apply the dispensed study medication in the morning QD into OU. See Sections 5.3 and 5.6 for more detail.

6. Response Measures and Summary of Data Collection Methods

6.1 Efficacy Measures

6.1.1 Primary Efficacy Measure

The primary efficacy measure will be mesopic, high contrast UNVA.

[REDACTED]

[REDACTED]

- [REDACTED]
 - [REDACTED]
 - [REDACTED]
- [REDACTED]
- [REDACTED]
 - [REDACTED]
 - [REDACTED]
- [REDACTED]
- [REDACTED]
- [REDACTED]

Approval Date: 18-Aug-2016

[Redacted]

- [Redacted]
- [Redacted]
- [Redacted]
- [Redacted]
- [Redacted]
- [Redacted]

[Redacted]

[Redacted]

[Redacted]

[Redacted]

Approval Date: 18-Aug-2016

[Redacted]

- | [Redacted]
- | [Redacted]
 - | [Redacted]
- | [Redacted]
- | [Redacted]
- | [Redacted]
- | [Redacted]
- | [Redacted]
- | [Redacted]
- | [Redacted]
- | [Redacted]

[Redacted]

- | [Redacted]
- | [Redacted]
- | [Redacted]
- | [Redacted]
- | [Redacted]

Approval Date: 18-Aug-2016

[Redacted text block containing multiple paragraphs of obscured content]

Approval Date: 18-Aug-2016

[Redacted]

[Redacted]

[Redacted]

[Redacted]

[Redacted]

[Redacted]

[Redacted]

[Redacted] epth of focus of the measured eye. More details will be outlined in the Procedure Manual.

Approval Date: 18-Aug-2016

[Redacted]

[Redacted]

[Redacted]

[Redacted]

[Redacted]

[Redacted]

[Redacted]

[Redacted]

[Redacted]

Approval Date: 18-Aug-2016

[Redacted text block]

[Redacted text block]

[Redacted text block]

[Redacted text block]

[Redacted text block]

[Redacted text block]

[Redacted text block]

[Redacted text block]

[Redacted text block]

[Redacted text block]

[Redacted text block]

Approval Date: 18-Aug-2016

[Redacted text block]

[Redacted text block]

[Redacted text block]

[Redacted text block]

[Redacted text block]

[Redacted text block]

[Redacted]	[Redacted]	[Redacted]	[Redacted]
[Redacted]	[Redacted]	[Redacted]	[Redacted]
[Redacted]	[Redacted]	[Redacted]	[Redacted]
[Redacted]	[Redacted]	[Redacted]	[Redacted]
[Redacted]	[Redacted]	[Redacted]	[Redacted]

[Redacted]	[Redacted]	[Redacted]	[Redacted]
[Redacted]	[Redacted]	[Redacted]	[Redacted]
[Redacted]	[Redacted]	[Redacted]	[Redacted]
[Redacted]	[Redacted]	[Redacted]	[Redacted]
[Redacted]	[Redacted]	[Redacted]	[Redacted]

Approval Date: 18-Aug-2016

[Redacted]

[Redacted]

[Redacted]	[Redacted]	[Redacted]
[Redacted]	[Redacted]	[Redacted]
[Redacted]	[Redacted]	[Redacted]
[Redacted]	[Redacted]	[Redacted]
[Redacted]	[Redacted]	[Redacted]

[Redacted]

[Redacted]	[Redacted]	[Redacted]
[Redacted]	[Redacted]	[Redacted]
[Redacted]	[Redacted]	[Redacted]
[Redacted]	[Redacted]	[Redacted]
[Redacted]	[Redacted]	[Redacted]

[Redacted]

[Redacted]

[Redacted]	[Redacted]	[Redacted]
[Redacted]	[Redacted]	[Redacted]
[Redacted]	[Redacted]	[Redacted]
[Redacted]	[Redacted]	[Redacted]
[Redacted]	[Redacted]	[Redacted]

[Redacted]

[Redacted]	[Redacted]	[Redacted]
[Redacted]	[Redacted]	[Redacted]
[Redacted]	[Redacted]	[Redacted]
[Redacted]	[Redacted]	[Redacted]
[Redacted]	[Redacted]	[Redacted]

Approval Date: 18-Aug-2016

[REDACTED]

[REDACTED]

[REDACTED] [REDACTED] [REDACTED] [REDACTED]

[REDACTED] [REDACTED] [REDACTED] [REDACTED]

[REDACTED] [REDACTED] [REDACTED] [REDACTED]

[REDACTED] [REDACTED] [REDACTED] [REDACTED]

[REDACTED] [REDACTED] [REDACTED] [REDACTED]

[REDACTED] [REDACTED] [REDACTED] [REDACTED]

[REDACTED]

[REDACTED] [REDACTED] [REDACTED]

[REDACTED] [REDACTED] [REDACTED]

[REDACTED] [REDACTED] [REDACTED]

[REDACTED] [REDACTED] [REDACTED]

[REDACTED] [REDACTED] [REDACTED]

[REDACTED]

[REDACTED]

[REDACTED]

[REDACTED]

[REDACTED]

[REDACTED]

[REDACTED]

[REDACTED]

[REDACTED]

[REDACTED]

[figure not shown]
[REDACTED]

[REDACTED]

[REDACTED]

[REDACTED]

Approval Date: 18-Aug-2016

Approval Date: 18-Aug-2016

[Redacted]

[Redacted]

[Redacted]

[Redacted]

[Redacted]

[Redacted]

[Redacted]

Approval Date: 18-Aug-2016

[Redacted]

[Redacted]

[Redacted]

[Redacted]

Approval Date: 18-Aug-2016

[Redacted]

[Redacted]

[Redacted]

[Redacted]

[Redacted]

[Redacted]

[Redacted]

[Redacted]

[Redacted]

[Redacted]

[Redacted]

[Redacted]

Approval Date: 18-Aug-2016

[Redacted]

[Redacted]

[Redacted]

[Redacted]

[Redacted]

[Redacted]

[Redacted]

[Redacted]

[Redacted]

[Redacted]

Approval Date: 18-Aug-2016

[Redacted text block]

[Redacted text block]

[Redacted text block]

[Redacted text block]

- [Redacted list item]
- [Redacted list item]
- [Redacted list item]
- [Redacted list item]
- [Redacted list item]
- [Redacted list item]
- [Redacted list item]
- [Redacted list item]
- [Redacted list item]
- [Redacted list item]
- [Redacted list item]
- [Redacted list item]
- [Redacted list item]
- [Redacted list item]

Approval Date: 18-Aug-2016

[REDACTED]

- [REDACTED]
- [REDACTED]
- [REDACTED]
- [REDACTED]
- [REDACTED]

6.6 Summary of Methods of Data Collection

This protocol will use eCRFs with remote data capture through a qualified third-party vendor. Data entered into the eCRF will correspond to, and be supported by, source documentation maintained at the sites. The investigator will be responsible for ensuring that data are properly recorded on each patient’s eCRF and related documents. Data will be entered on the eCRFs in a timely manner and on an ongoing basis. An IxRS will be used to assign patient identification numbers, randomize patients, and manage study medication inventory. Data will be transferred to Allergan on a periodic basis throughout the study.

7. Statistical Procedures

One database lock is planned at the completion of the study. A detailed analysis plan (AP) will be approved prior to database lock.

7.1 Analysis Populations

The modified intent-to-treat (mITT) population will be defined as all randomized patients with a baseline and at least 1 postbaseline assessment of mesopic, high contrast UNVA and will be analyzed as randomized. The efficacy variables will be analyzed using the mITT population.

The safety population will be defined as all patients who received at least 1 dose of study treatment. Safety analyses will be performed on an as-treated basis. All safety measures will be analyzed using the safety population.

Approval Date: 18-Aug-2016

In general, continuous data will be summarized with descriptive statistics (number of patients, mean, standard deviation, median, minimum, and maximum) and will be analyzed using analysis of covariance (ANCOVA) or 2-sample t-tests. Categorical variables will be summarized by sample size (N), frequency count and percent, and will be analyzed using Pearson's chi-square, Fisher's exact, or the Cochran-Mantel-Haenszel (CMH) test.

There will be no imputation of missing data for all analyses.

7.2 Collection and Derivation of Primary and Other Efficacy Assessments

7.2.1 Primary Efficacy Variable

The primary efficacy variable will be the weighted average change from baseline in mesopic, high contrast UNVA lines at day 28 in the nondominant eye. Baseline will be the hour 0 measure at day 1.

[REDACTED]

[REDACTED]

[REDACTED]

[REDACTED]

[REDACTED]

[REDACTED]

[REDACTED]

[REDACTED]

[REDACTED]

[REDACTED]

[REDACTED]

[REDACTED]

[REDACTED]

[REDACTED]

[REDACTED]

[REDACTED]

[REDACTED]

[REDACTED]

[REDACTED]

[REDACTED]

[REDACTED]

[REDACTED]

Approval Date: 18-Aug-2016

- [REDACTED]
- [REDACTED]
- [REDACTED]
- [REDACTED]
- [REDACTED]
- [REDACTED]
- [REDACTED]

- [REDACTED]
 - [REDACTED]
 - [REDACTED]
 - [REDACTED]
 - [REDACTED]
 - [REDACTED]
 - [REDACTED]
 - [REDACTED]
 - [REDACTED]
 - [REDACTED]

- [REDACTED]
 - [REDACTED]
 - [REDACTED]
 - [REDACTED]
 - [REDACTED]
 - [REDACTED]
 - [REDACTED]
 - [REDACTED]
 - [REDACTED]

Approval Date: 18-Aug-2016

- █ [REDACTED]
- █ [REDACTED]
- █ [REDACTED]
- █ [REDACTED]
 - █ [REDACTED]
 - █ [REDACTED]
 - █ [REDACTED]
 - █ [REDACTED]
 - █ [REDACTED]

7.3 Hypothesis and Methods of Analysis

In general, continuous data will be summarized with descriptive statistics (number of patients, mean, standard deviation, median, minimum, and maximum) and will be analyzed using ANCOVA techniques or 2-sample t-tests (for between-group comparisons) and paired t-tests (for within-group analyses). Categorical variables will be analyzed using the CMH test.

There will be no adjustment of type 1 error rate for the multiple tests. There will be no imputation of missing data for all analyses.

7.3.1 Primary Efficacy Analyses

For the primary efficacy analysis, the weighted average change from baseline will be analyzed by ANCOVA with treatment group, age group, and iris color as fixed effects. A detailed algorithm for the derivation of the primary efficacy variables will be documented in the AP.

█ [REDACTED]

█ [REDACTED]

█ [REDACTED]

█ [REDACTED]

Approval Date: 18-Aug-2016

[Redacted text block]

[Redacted text block]

[Redacted text block]

[Redacted text block]

[Redacted text block]

[Redacted text block]

[Redacted text block]

7.4 Subgroup Analyses

Subgroup analyses will be performed for the primary efficacy variable by UNVA at baseline (20/40 to 20/80 and 20/100 to 20/200), age group, and iris color (brown or not brown).

7.5 Sample Size Calculation

A sample size of approximately 150 patients will be randomized in a 1:1:1:1:1 ratio into 1 of the 5 study groups. Approximately two-thirds of the enrolled patients will be younger patients (≤ 50 years old), and approximately one-third of the enrolled patients will be older patients (> 50 years old).

Approval Date: 18-Aug-2016

From the Study 199201-007 results, the treatment effect for the younger patients was on average 1.98 lines of change in mesopic, high contrast UNVA, with standard deviations for active and vehicle of 1.12 and 1.01, respectively. For older patients, the treatment effect was on average 0.72 lines of change in mesopic, high contrast UNVA, with standard deviations for active and vehicle of 1.87 and 1.15, respectively. The treatment effect for the younger patients was on average 1.02 lines of change in photopic, high contrast UNVA, with standard deviations for active and vehicle of 1.42 and 0.67, respectively. For older patients, the treatment effect was on average 0.27 lines of change in photopic, high contrast UNVA, with standard deviations for active and vehicle of 1.10 and 0.93, respectively.

Accounting for a 12.5% dropout rate, 26 patients per treatment group will provide 99% power to observe a difference between an active group and the vehicle group for ≥ 1 line of change from baseline in mesopic, high contrast UNVA and 68% power for ≥ 1 line of change from baseline in photopic, high contrast UNVA, with a type 1 error of 0.05.

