Sample Size Calculation:

A sample size of approximately 150 patients will be randomized in a 1:1:1:1:1 ratio into 1 of the 5 study groups. Approximately two-thirds of the enrolled patients will be younger patients (≤ 50 years old), and one-third of the enrolled patients will be older patients (> 50 years old).

[figure not shown]
From the Study 199201-007 results, the treatment effect for the younger patients was on average 1.98 lines of change in mesopic, high contrast UNVA, with standard deviations for active and vehicle of 1.12 and 1.01,

respectively. For older patients, the treatment effect was on average 0.72 lines of change in mesopic, high contrast UNVA with standard deviations for active and vehicle of 1.87 and 1.15 respectively. The treatment effect for the younger patients was on average 1.02 lines of change in photopic, high contrast UNVA, with standard deviations for active and vehicle of 1.42 and 0.67, respectively. For older patients, the treatment effect was on average 0.27 lines of change in photopic, high contrast UNVA, with standard deviations for active and vehicle of 1.10 and 0.93, respectively.

[figure not shown]
Accounting for a 12.5% dropout rate, 26 patients per treatment group will provide 99% power to observe a difference between an active group and the vehicle group for ≥ 1 line of change from baseline in mesopic, high contrast UNVA and 68% power for ≥ 1 line of change from baseline in photopic, high contrast UNVA, with a type 1 error of 0.05.

Approval Date: 18-Aug-2016

[figure not shown]
Approval Date: 18-Aug-2016

[figure not shown]
Approval Date: 18-Aug-2016

[figure not shown]
Approval Date: 18-Aug-2016

[figure not shown]
Approval Date: 18-Aug-2016

[figure not shown]
Approval Date: 18-Aug-2016

[figure not shown]

Approval Date: 18-Aug-2016

Approval Date: 18-Aug-2016

Approval Date: 18-Aug-2016

1. Background and Clinical Rationale

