5.1.1.1.3 Statistical Methodology

The methodologies defined below apply as specified to individual endpoints defined in this SAP. When indicated, 95% two-sided confidence intervals and two-sided p-values will be presented. Individual endpoint analyses may specify exceptions (additions or deletions) to these general definitions.

Table 5-2 Statistical Methodology

| Methodology | Description |
|-----------------------------|---|
| M1 Categorical counts | 
 Number of patients in individual categories 
 Patients with ≥ 1 qualifying event counted once per individual category |
| M2 Categorical descriptives | 
 Number and percentage of patients in individual categories 
 Patients with ≥ 1 qualifying event counted once per individual category (Optional) N included if percentage denominator \neq number of patients in the population (standard percentage denominator). |
| M3 PCS descriptives | 
 Number and percentage of patients meeting potentially clinically significant (PCS) criteria 
 Patients with ≥ 1 qualifying event counted once per PCS category Percentage denominator = number of patients with non-missing baseline and ≥ 1 non-missing postbaseline assessment Unevaluable assessments considered missing |
| M4 Continuous descriptives | 
 N included, mean, standard deviation (SD), median, minimum, maximum N included = patients with non-missing value |
| M5 CFB descriptives | 
 Continuous descriptives for baseline, postbaseline, and change from baseline (CFB) values N included = patients with non-missing values at both baseline and the specified postbaseline analysis visit |
| M6 CFB ANCOVA | 
 Continuous descriptives and standard error (SE) for baseline, postbaseline, and CFB values Estimates derived from mixed model for CFB value controlling for treatment group and covariates (baseline UNVA severity, iris color and age group) 
 Least squares (LS) means and standard errors P-values and confidence intervals from contrast t-test comparing active AGN-199201 treatment groups vs AGN-199201 vehicle N included = patients with non-missing values at both baseline and the postbaseline analysis visit |

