5.1.2 Determination of Sample Size

A sample size of approximately 150 patients will be randomized in a 1:1:1:1:1 ratio into 1 of the 5 study groups. Approximately two-thirds of the enrolled patients will be younger patients (≤ 50 years old), and approximately one-third of the enrolled patients will be older patients (> 50 years old).

From the Study 199201-007 results, the treatment effect for the younger patients was on average 1.98 lines of change in mesopic, high contrast UNVA, with standard deviations for active and

vehicle of 1.12 and 1.01, respectively. For older patients, the treatment effect was on average 0.72 lines of change in mesopic, high contrast UNVA, with standard deviations for active and vehicle of 1.87 and 1.15, respectively. The treatment effect for the younger patients was on average 1.02 lines of change in photopic, high contrast UNVA, with standard deviations for active and vehicle of 1.42 and 0.67, respectively. For older patients, the treatment effect was on average 0.27 lines of change in photopic, high contrast UNVA, with standard deviations for active and vehicle of 1.10 and 0.93, respectively.

Accounting for a 12.5% dropout rate, 26 patients per treatment group will provide 99% power to observe a difference between an active group and the vehicle group for lines of change from baseline in mesopic, high contrast UNVA, and 68% power for lines of change from baseline in photopic, high contrast UNVA, with a type I error of 0.05

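### The stated 99% (mesopic) and 68% (photopic) power belong to differences of about 1.56 and 0.77 lines, not to the 1 line written in Protocol 7.5

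*Protocol*

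**What the plan says.** Protocol 7.5 takes its inputs from Study 199201-007 as mean effects with SDs, separately by age. For example, "the treatment effect for the younger patients was on average 1.98 lines of change in mesopic, high contrast UNVA", with SDs of 1.12 (active) and 1.01 (vehicle). It also fixes the age mix: "Approximately two-thirds of the enrolled patients will be younger patients (≤ 50 years old"). For the mesopic outcome it then claims "99% power to observe a difference between an active group and the vehicle group for ≥ 1 line of change from baseline in mesopic". A second claim of the same form covers the photopic outcome: "68% power for ≥ 1 line of change from baseline in photopic, high contrast UNVA, with a type 1 error of 0.05". The Protocol Summary makes both claims too.

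SAP 5.1.2 repeats the inputs and both percentages, but the 1-line qualifier is gone: "99% power to observe a difference between an active group and the vehicle group for lines of change from baseline in mesopic". No other difference is named.

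The primary variable (Protocol 7.2.1) is a mean: the "weighted average change from baseline in mesopic, high contrast UNVA lines at day 28 in the nondominant eye". Under Protocol 7.3.1 it is "analyzed by ANCOVA with treatment group, age group, and iris color as fixed effects". The SAP's CFB ANCOVA method (M6, section 5.1.1.1.3) adds baseline UNVA severity as a covariate and takes "P-values and confidence intervals from contrast t-test comparing active AGN-199201 treatment groups vs AGN-199201 vehicle". Neither sample-size section states a pooled SD, an age-weighted effect or the test used.

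**The concern.** The two percentages cannot both belong to one common difference. At the same difference and the same group size, the outcome with the smaller SD has the higher power. On the plan's own figures the pooled photopic SD (about 1.1) is smaller than the mesopic SD (about 1.25 to 1.3), yet the stated photopic power is 31 points lower.

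What is at stake is how a single dose group is read. The Protocol tells its reader that a group with a true 1-line mesopic advantage over vehicle would almost certainly reach significance, so a non-significant group would look like good evidence against a 1-line effect. If the true power is below about 81%, that inference is much weaker.

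**Working it through.** **Inputs** (Protocol 7.5, repeated in SAP 5.1.2)

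- 26 per group (30 × 0.875 = 26.25); type 1 error 0.05. Two-sided testing comes from SAP 5.1.1.1.3. Protocol 7.3 makes no multiplicity adjustment, so power is per comparison.
- Age weights 2/3 (≤ 50 years) and 1/3 (> 50 years).
- Mesopic: effect 1.98 (SDs 1.12 active, 1.01 vehicle) younger; 0.72 (1.87, 1.15) older.
- Photopic: effect 1.02 (1.42, 0.67) younger; 0.27 (1.10, 0.93) older.

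**Step 1. Age-weighted effects**

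- Mesopic: 2/3 × 1.98 + 1/3 × 0.72 = 1.56 lines.
- Photopic: 2/3 × 1.02 + 1/3 × 0.27 = 0.77 line.

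**Step 2. Pooled SDs.** The documents give none, so the pooling is an assumption and two versions are shown.

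- Mesopic variances: active 2/3 × 1.12² + 1/3 × 1.87² = 2.002; vehicle 2/3 × 1.01² + 1/3 × 1.15² = 1.121. Within-age SD = √((2.002 + 1.121)/2) = 1.250. Adding the between-age spread of the effect to the active arm, 2/3 × 1/3 × (1.98 − 0.72)² = 0.353, gives 1.318.
- Photopic variances: active 1.748, vehicle 0.588. Within-age SD = 1.081. Adding 2/3 × 1/3 × (1.02 − 0.27)² = 0.125 gives 1.109.

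**Step 3. Two-arm t-test.** Standard error = SD × √(2/26); noncentrality = difference / standard error; 50 degrees of freedom; two-sided 0.05.

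| Outcome | SD | Power at planning effect | Power at 1 line | Stated |
|---|---|---|---|---|
| Mesopic | 1.250 | 99.3% (1.56 / 0.347 = 4.50) | 80.8% (1 / 0.347 = 2.89) | 99% |
| Mesopic | 1.318 | 98.7% (1.56 / 0.366 = 4.27) | 76.5% (1 / 0.366 = 2.74) | 99% |
| Photopic | 1.081 | 71.2% (0.77 / 0.300 = 2.57) | 90.5% (1 / 0.300 = 3.34) | 68% |
| Photopic | 1.109 | 69.0% (0.77 / 0.308 = 2.50) | 89.0% (1 / 0.308 = 3.25) | 68% |

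The stated figures are recovered at the planning effects: mesopic closely, photopic within about 1 to 3 points. A Welch test with SD 1.109 gives 68.5% for photopic. At 1 line neither figure is recovered.

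**Step 4. Does another pooling rescue the 1-line wording?** At 1 line and 26 per group, 99% power needs a common SD of about 0.825, below all four listed mesopic SDs (1.01 to 1.87). Power of 68% needs about 1.457, above all four listed photopic SDs (0.67 to 1.42). No weighting of the plan's own SDs gives either figure.

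**Step 5. Five-group error term.** The planned ANCOVA with contrasts can be read as using a residual variance pooled over all five groups. This was simulated with 40,000 trials: 17 younger and 9 older patients per group, four active groups all with the listed active SDs, a model with treatment and age group, and a contrast against vehicle. Iris color and baseline severity were left out because no inputs exist for them.

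- At 1 line: about 77% mesopic and 86% photopic.
- At the age-specific planning effects: 98.7% mesopic and 60.8% photopic. The stated 68% therefore fits a two-arm test better.
- With a 1-line mesopic effect in all three bilateral groups, at least one comparison is significant in about 95% of trials.

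**The case against.** **At least 1 line includes 1.56.** A mesopic planning effect of 1.56 lines does satisfy the phrase, so on that side the wording might be called loose rather than false. But the lowest power over that range is at 1 line, about 76-81%. The same phrase is used for photopic, where the planning effect of 0.77 lies below 1.

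**A responder reading.** The phrase might mean patients who gain at least 1 line. Vehicle means are not given, so arithmetic alone cannot exclude this. Assuming normal data and one common vehicle mean between −0.5 and 1.0 line, power runs from 81% to 98% mesopic and from 33% to 79% photopic, and no value tried gives both stated figures. If the vehicle means may vary, 68% photopic becomes attainable while mesopic reaches at most 98.5%. The stronger answer is the text itself: the inputs are means and SDs, no responder rates are given, and the primary variable is a mean change.

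**The SAP has dropped the phrase.** It has, but it names no difference instead, and the Protocol text stands.

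**Little depends on it.** This has real weight. The primary comparison is mesopic, and its 99% is right at the planning effect. The hypothesis in Protocol 2.2 needs only one bilateral combination to succeed, so the 95% result in the working limits the consequence for the trial as a whole. Also, 1.56 and 0.77 are inferred from the inputs and not printed, and the photopic match is approximate. The sponsor should therefore confirm them.

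**Conclusion.** The concern holds. The percentages in Protocol 7.5 and the Protocol Summary are attached to the wrong difference. For one active group against vehicle at a true 1-line difference, power is 76.5-80.8% mesopic by a two-arm test (about 77% with five-group error), not 99%; the overstatement is about 18 to 22.5 points (99 − 80.8 = 18.2; 99 − 76.5 = 22.5). Photopic power is 89.0-90.5% two-arm (about 86% five-group), not 68%.

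The exact ranges rest on a difference-in-means reading, 26 evaluable patients per group, a two-sided 0.05 test, the 2/3 to 1/3 age mix and the Study 199201-007 SDs; the five-group figures also assume equal SDs in the active groups. The direction does not depend on how the SDs are pooled. This is an error in the stated justification of the sample size. It should be corrected, but it does not show that the trial is too small for its planning effect.

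**What to change.** In the Protocol Summary and Protocol 7.5, replace both 1-line phrases with the differences the percentages belong to: 1.56 lines mesopic and 0.77 line photopic, for one active group against vehicle at a two-sided type 1 error of 0.05. The sponsor should confirm these values from its own calculation, and state the pooled SDs and whether the test was two-arm or the five-group ANCOVA contrast. It should also give the per-comparison power at 1 line under that test. Name the same differences in SAP 5.1.2 so that the documents agree.

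The cost is wording in two Protocol places and one SAP place. The 99% stays, but it no longer supports a claim about a 1-line mesopic difference. Sample size, endpoint and analysis are unchanged.
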